2.3 Schedule of Activities (SOA)

Table 3. Schedule of Activities for UG3/Phase 1 Pilot/Feasibility (Aim 1) and UH3/Phase 2 RCT (Aim 2)	Screener	BL	Enrollment call	Intervention Sessions	3m to up to the start of 6m assessment	6m + 3m (UH3/Phase 2 only)
Feasibility of recruitment, enrollment, intervention, and data collection rates (see 2.4 Milestones for more detail)	x	x	x	x	x	
Inclusion/Exclusion criteria	x		x			
Demographic (including core SDH measures)		x				
Consent			x			
Enrollment/randomization			x			
Primary Outcome						
Pain interference (BPI)	x	x			x	x
Secondary Outcomes						
Pain intensity (BPI)		x			x	x
Pain impact (GCPS-R)		x			x	x
Quality of life (WHO QOL 2 item & EQ5D5L)	x				x	x
Use of opioids (self-report, EHR)	x				x	x
Physical function (PROMIS)	x				x	x
Sleep (PROMIS)	x				x	x
Fatigue (PROMIS)	x				x	x
Anxiety (GAD2)	x				x	x
Depression (PHQ2)	x				x	x
PTSD (PC-PTSD-5)		x			x	x
Participation in social roles and activities (PROMIS)		x			x	x
Global improvement and satisfaction (PGIC)					x	x
Use of CIH and non-pharmacological pain management		x			x	x
Adverse events				x	x	x
Mediation Measures						
Pain catastrophizing (PCS)		x			x	x
Pain management self-efficacy (PROMIS)	x				x	x
Perceived stress (PSS)	x				x	x
Body Awareness (MAIA)	x				x	x
Other Measures						
Substance Use Screener (TAPS)		x			x	x
Intervention-related measures*					x	x

BL=baseline; 3m=3 months; 6m=6 months; SDH=social determinants of health; BPI=brief pain inventory; GCPS-R=graded chronic pain scale-revised; WHO QOL=World Health Organization Quality of Life; EQ5D5L=5-level Euro Quality of Life-5D; PROMIS=patient-reported outcomes measurement information system; GAD2=generalized anxiety disorder; PHQ2=patient health questionnaire depression scale; PC-PTSD-5=PTSD checklist for DSM-5; EHR=electronic health record; PCS=pain catastrophizing scale; PSS=perceived stress scale; MAIA=multidimensional assessment of interoceptive awareness; TAPS=Tobacco Alcohol Prescription medications and other Substance; *Intervention related measures are also considered patient-level RE-AIM/PRISM measures.

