The Need for Whole Health Approaches to Pain Management. Pain, like most health conditions, has become widely recognized as more than a physical phenomenon. It is a complex condition influenced by interrelated biophysical, psychological, and social (BPS) factors.^{18,19} Pain is frequently associated with psychological risk factors including poor cognitive and emotional coping strategies, depression, catastrophizing, and fear avoidance behaviors.^{45,46} There is also growing evidence that social determinants of health are associated with greater likelihood of chronic pain and poorer outcomes.⁴⁷⁻⁴⁹ Lack of social support,⁵⁰⁻⁵² and occupation and related factors such as physical workload, education, injury compensation, and dissatisfaction can also have a negative effect on pain.^{43,46} Poor quality relationships, social stressors (e.g., due to racism, ostracism, injustice, invalidation, isolation), and low income and education status also have been shown to contribute to poor outcomes.^{43,53,54} Further, there is growing recognition of the important intersections among trauma, violence, substance use, and pain.⁵⁵ Veterans in the VA healthcare system are especially impacted by these factors; they have lower levels of income and education and higher levels of trauma exposure compared to non-Veterans and Veterans not enrolled in VA care.^{56,57} Compared to men, female VA patients are more likely to report history of interpersonal trauma, military sexual trauma, mood disorders, and anxiety disorders,^{10,44} all of which can adversely affect treatment outcomes. Rural-dwelling female VA patients are even more impacted, with a high probability (50%) of interpersonal and/or sexual traumas,⁵⁸ high rates of emotional distress, and low levels of social support.^{10,11,58}

To reduce the burden of pain, patients require greater access to evidence-based care that addresses their “whole-person” or biopsychosocial needs.⁵⁹⁻⁶¹ There has been a growing recognition that pain, like other chronic health conditions, requires ongoing attention to lifestyle factors and engagement in effective self-management.^{62,63} While patients recognize the need

for self-management strategies, they often need support and validation to initiate and maintain optimal self-care.^{64,65}

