Our power calculation uses the Brief Pain Inventory (BPI) interference scores over the entire follow-up period as the primary outcome measure. The primary outcome uses a repeated measures approach that takes into account assessments at 3 and 6 months with a single test of significance. Secondary outcomes will evaluate the time points separately. For our primary analysis we estimate up to 20% attrition, so at least 500 people will need to be randomized to obtain a sample of 400 people with complete data. 200 participants in each arm will yield 90% power, with an alpha of 0.05, to reject the null hypothesis of equal means over the repeated follow-up time points (i.e., 3 and 6 months) if the arms differ by an effect size of 0.3 or greater. This includes a conservative estimate that the repeated outcome measures are highly correlated ($r=0.7$) and even with only 1 time point there is power to detect effect sizes of 0.32. Analyses that are stratified by subgroups as small as 70 people per arm (i.e., equivalent to restricting to only women or minority Veterans) would have approximately 90% power to detect differences of 0.50. However, these would only be exploratory in nature and not adjusted for multiple comparisons. While our goal is to achieve 500 randomized participants, our intervention will roll out in large waves so precisely hitting a randomized sample number is difficult. Therefore, we asked for an administrative IRB approval to exceed this goal and enroll up to 550 participants.

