We will use an intention-to-treat approach. Preliminary descriptive analyses will summarize the distributions of the baseline measures across treatment arms overall and will similarly assess the outcome distributions across assessment time points (i.e., baseline, 3, and 6 months). We will summarize the completeness of the self-reported outcome assessments and examine associations between completeness and baseline measures as well as the association with secondary outcome assessments that are collected from the electronic medical record (e.g., medications, health care utilization related to pain treatment). Initial analyses will use all available follow-up data and subsequent sensitivity analyses will examine the potential effect of response bias. For analyses of the primary outcome, all repeated measurements of the BPI interference score will be fitted in a mixed model for repeated measures as a function of the group assignment, while controlling for time points and baseline values of the outcome as fixed effects, with participants as random effects. Between-group differences over the entire follow-up period (average of 3 and 6 months) will be the primary test of treatment group differences. Between-group differences will be estimated for each of the individual time points as secondary outcomes. Similar to the methods described above for the primary analyses, weighted selection model analyses will examine the sensitivity of the initial results to response biases. To do this, we will fit a series of weighted selection model analyses. Each analysis will use an expectation-maximization algorithm to estimate weights to assign to potential values of the missing outcomes for use in the regression model. The secondary outcomes will be similarly analyzed

using the same linear mixed effect models for normal continuous measures and appropriate generalized linear mixed effect models for non-normal measures.

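### The primary model adjusts only for time point and baseline BPI interference; prespecifying other prognostic factors already collected before randomization would be a nearly free improvement

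*Combined protocol and SAP*

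**What the plan says.** Section 5.8 (UH3/Phase 2, Aim 1, RCT) models the repeated BPI interference scores as a function of group, "while controlling for time points and baseline values of the outcome as fixed effects, with participants as random effects". The test is a single one: "Between-group differences over the entire follow-up period (average of 3 and 6 months) will be the primary test of treatment group differences". No other baseline variable appears in that model.

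Table 3 in section 2.3 marks the following in the screener or baseline column, ahead of the enrollment call at which randomization takes place: the row "Demographic (including core SDH measures", pain intensity, PROMIS physical function, PHQ-2, PC-PTSD-5 and the Pain Catastrophizing Scale (PCS). Section 3.2 names depression and catastrophizing among psychological risk factors associated with pain, and cites "growing evidence that social determinants of health are associated with greater likelihood of chronic pain and poorer outcomes".

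On missing data, section 5.8 plans to "examine associations between completeness and baseline measures" and to relate completeness to outcomes taken from the electronic record. It then plans a series of weighted selection models, with weights estimated by an EM algorithm, to test sensitivity to response bias. It does not say which covariates those models contain. Sex and race/ethnicity enter only the exploratory subgroup, interaction and multivariable analyses.

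**The concern.** Two things are at stake.

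The first is precision. Baseline variables that predict follow-up BPI beyond baseline BPI itself would narrow the interval for the one primary contrast, and the data will already be in hand.

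The second is the missing-data assumption. An all-available-data mixed model gives an unbiased contrast when non-response is random given what the model conditions on: arm, visit, baseline BPI and any observed follow-up BPI. If distress or social circumstances also drive non-response, and do so differently in the two arms, the primary estimate is not protected. The arms do differ in contact: nine weekly coach-led sessions with follow-up of absentees in RAMP, against surveys only in Usual Care (section 5.1.2). Up to 20% attrition is allowed for.

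**Working it through.** **Inputs from section 5.8.** "200 participants in each arm will yield 90% power, with an alpha of 0.05"; effect size 0.3; correlation of 0.7 between the 3- and 6-month scores; 20% attrition, so 500 randomized gives 400. Sidedness is not stated. Two-sided reproduces the plan's figure, while one-sided would give 94.6%.

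**Assumed, because the documents give no value.** The share R² of variance explained beyond baseline BPI (0.02 to 0.15), the correlation of baseline with follow-up BPI (0.5), and how non-response depends on a baseline factor.

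**1. The plan's own figure.** The variance of the mean of two visits is (1 + 0.7)/2 = 0.85. SE = sqrt(2 × 0.85/200) = 0.0922. Power = Φ(0.3/0.0922 − 1.96) = 90.2%. The stated 90% reproduces with no covariate credit, not even for baseline BPI.

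**2. Precision, with 0.3 on the residual scale of the planned model.** Multiply 0.85 by (1 − R²). The effective number of completers is 400/(1 − R²).

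| R² | Power | Effect detectable at 90% | Equivalent completers |
|---|---|---|---|
| 0 | 90.2% | 0.299 | 400 |
| 0.02 | 90.8% | 0.296 | 408 |
| 0.05 | 91.6% | 0.291 | 421 |
| 0.10 | 92.9% | 0.284 | 444 |
| 0.15 | 94.2% | 0.276 | 471 |

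**3. Precision, with 0.3 in raw SD and baseline correlation 0.5.** Residual variance is 0.85 − 0.25 = 0.60, so SE = sqrt(2 × 0.60/200) = 0.0775 and power is already 97.2%. R² of 0.02 to 0.15 moves it to 97.5-98.7%, a gain of 0.3 to 1.5 points. On this scale, partial coefficients of 0.1, 0.2 and 0.3 per SD of the added score correspond to R² of 0.01/0.60 = 1.7%, 0.04/0.60 = 6.7% and 0.09/0.60 = 15%.

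**4. Bias from non-response on one omitted factor.** Bias = partial coefficient × difference between arms in the factor's mean among responders. Non-response follows a logistic model, at 20% per arm except in the second row.

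| Odds ratio for non-response per SD, RAMP vs Usual Care | Mean difference | Bias for coefficient 0.1 to 0.3 |
|---|---|---|
| 1.49 vs 1.49 | 0 | 0 |
| 1.49 vs 1.49, but 25% vs 15% non-response | −0.038 | −0.004 to −0.011 |
| 1.49 vs 1.00 | −0.078 | −0.008 to −0.023 |
| 1.49 vs 0.67 | −0.155 | −0.016 to −0.047 |
| 2.23 vs 0.45 (extreme) | −0.290 | −0.029 to −0.087 |

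Swapping the arms reverses the sign.

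**5. Effect on the test.** In the 1.49 vs 0.67 case with coefficient 0.2, the bias is 0.031/0.0775 = 0.40 SE. A normal approximation then gives a type I error of Φ(−1.96 + 0.40) + Φ(−1.96 − 0.40) = 6.9%. A simulation with 250 per arm gave 7.6%, and about 5% once the factor was in the model.

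**The case against.** The strongest reply is that nothing is broken. Adjusting for the baseline outcome is a sound prespecified analysis, the sample size does not rely on more, and section 5.2.2 states no stratified randomization, so no stratification factor is missing from the model. All of that stands.

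A reader might infer that bias from non-response goes uncorrected. The documents do not support this: section 5.8 plans both the completeness analysis and the weighted selection models. What remains is that those models' covariates are unlisted and that the correction does not reach the primary estimate.

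A reader might also infer that the bias would favour RAMP. No document reports arm-differential non-response, and the direction depends entirely on the pattern assumed. The size may be smaller too. The 20% is a planning ceiling, and the similar earlier trial had 86% follow-up at 12 months. At 14% non-response, with odds ratios of 1.5-2 in RAMP only and coefficients of 0.1-0.2, the bias is about 0.005-0.018 SD, less than a quarter of one SE.

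Finally, section 3.2 reports associations with pain. It does not show that these factors predict follow-up BPI given baseline BPI, and two that it names, coping and fear avoidance, have no row in Table 3. This is why R² is shown as a range starting at 0.02. None of these objections identifies a real cost to making the change.

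**Conclusion.** The point holds as a recommended improvement. The primary analysis is valid and powered as stated. It forgoes a modest gain: about 0.6 to 4 power points if 0.3 is on the residual scale and R² is 0.02 to 0.15, or about one point if 0.3 is in raw SD with a baseline correlation of 0.5. It also makes the missing-at-random assumption of the primary estimate narrower than it need be. The exposure is roughly 0.01-0.05 SD in either direction in mild to moderate scenarios, up to about 0.09 SD in an extreme one, and zero if the factor acts equally in both arms at equal rates, set against the 0.3 SD the trial is designed to detect. Prognostic strength and differential non-response are both assumptions. Adjustment removes only what the measured factors capture.

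**What to change.** In section 5.8, before database lock:

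- Prespecify a short list of pre-randomization covariates for the primary model and the matching secondary models. For example: age, sex, race/ethnicity, VISN, baseline pain intensity, physical function, PHQ-2, PC-PTSD-5, baseline PCS and one named social-determinants measure.
- Use baseline values only. PCS is also a mediator in this plan, so its follow-up values must stay out of the model.
- Fill missing covariate values by single imputation that ignores arm.
- Keep the model with baseline BPI alone as a sensitivity analysis.
- Use the same covariates in the weighted selection models, adding any baseline measure found to be associated with completeness.

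The cost is wording plus about ten degrees of freedom out of roughly 400 participants. No new data, visits or sample size are needed. Investigators are to be blinded to outcomes until lock (section 5.2.2) and no interim analyses are planned (section 6.2.1), so a list fixed before lock would be credible.

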2.4 Milestones

Abbreviated title: Rural Veterans Applying Mind Body Skill for Pain (RAMP)
Version date: 8/22/25

2.4.1 UG3/Phase 1 Milestones

UG3/Phase 1 Milestone Timeline (Years 1-2 of Project)	Year 1												Year 2												
	Month	1	2	3	4	5	6	7	8	9	10	11	12	13	14	15	16	17	18	19	20	21	22	23	24
Quarter	1	1	1	2	2	2	3	3	3	4	4	4	5	5	5	6	6	6	7	7	7	8	8	8	
Agreements and Regulatory Approvals																									
All necessary approvals received (IRB, NIH, DSMB) for all required protocols and plans (e.g., clinical protocol; accrual/retention plan, data and safety monitoring plans)																									X
Advisor Engagement																									
Community-based partners named																									X
Multi-level (patient, community, and VA) advisor/partner panels established																									X
Multi-level advisor assessments (of implementation-related barriers and facilitators, resource needs, and other RE-AIM/PRISM domains) collected and analyzed (n = 35-50)																									X
Pilot Study																									
Recruitment and Enrollment																									
40 rural-dwelling VA patients recruited																									X
At least 35% female and 35% racial/ethnic minority patients recruited																									X
Experimental Intervention																									
75% satisfied with RAMP program																									X
75% of intervention participants attend/engage with recommended # of sessions (≥ 7/12)																									X
Health Coach Facilitators deliver 90% of session activities 90% of the time																									X
Data Collection																									
>80% complete post-treatment data collection (at 3 months)																									X
Key: DSMB=Data and Safety Monitoring Board; IRB=Institutional Review Board; NIH=National Institutes of Health; VA=Veterans Healthcare Administration.																									

Successful completion of these milestones will establish the feasibility of our processes and ensure that we are prepared for the proposed UH3/Phase 2 randomized hybrid type 2 effectiveness-implementation pragmatic clinical trial of RAMP.

2.4. UH3/Phase 2 Milestones

UH3/Phase 2 Timeline (Years 3-5 of Project).	Quarter
Administrative	
All staff hired and trained	10
Manual of Procedures (MOP) finalized	12
100% compliance with PRISM Program policies and practices, including workgroup participation (Annual)	12, 16, 20

100% compliance with Protocol (Annual)	12, 16, 20
100% compliance with Data and Safety Monitoring Plan (Annual)	12, 16, 20
Investigator Steering Committee meets monthly & project teams meet 1-4X/monthly (Annual)	12, 16, 20
All staff maintain "trained" status each year including required human subjects training (Annual)	12, 16, 20
Results submitted to clinicaltrials.gov	20
Final report submitted	20
UH3 Aim 1: Randomized Trial	
Recruitment and Enrollment	
Study Open to Enrollment	10
50% total sample enrolled (w/ completed baseline) per year (35% female; 35% racial/ethnic minority)	13, 17
Intervention delivery	
50% total sample participate in intervention per year (Annual)	15, 19
75% satisfied with RAMP program	19
75% of intervention participants attend/engage with recommended # of sessions ($\geq 6/9$)	19
15% of intervention sessions fidelity checked and Health Coach Facilitators achieve high fidelity rates ($> 90\%$)	18
Data assessment and retention (Assess all participants at 3- and 6-month timeframes)	
Data collected at 3 and 6 months for 50% of participants per year	15, 19
> 80% of participants each year retained for primary outcome at 6 months	15, 19
Data analysis	
Final dataset transferred to statisticians for data analysis	20
Aim 1 data analysis completed	20
UH3 Aim 2: Implementation Aim	
Meet with patients and community advisors at least 3X/year	12, 16, 20
Meet with VA advisors at least 1X/year.	12, 16, 20
Aim 2a. Conduct mixed-methods assessments of advisor and randomized trial participant views of implementation-related barriers and facilitators, resource needs, and other RE-AIM/PRISM domains	
Aim 2a data collection and data analysis completed	20
Aim 2b. Work with advisors to co-create additional plausible strategies for overcoming barriers to implementation of RAMP in the national VA healthcare system	
Aim 2b process plans and implementation strategies completed	20
Aim 2c: Conduct budget impact analyses using models informed by advisor views to inform future decision making	
Aim 2c budget impact analysis completed	20
Implementation and Dissemination	
Experimental intervention Adaptations	
Necessary intervention adaptations based on results completed	20
Dissemination and manuscript writing	
Design manuscript submitted	11
Main trial results manuscript submitted	20
Main implementation results manuscript submitted	20
Ongoing learnings disseminated via channels identified by multi-level advisors	12, 16, 20

3.0 Introduction

3.1 Study Rationale

This project addresses the significant challenge of implementing effective, non-opioid interventions for chronic pain management in rural and remote dwelling Veteran populations. Pain is a complex biophysical, psychological, and social (BPS) condition and there is a growing evidence base to support several complementary and integrative health (CIH) approaches, which can address pain in a more holistic way. While the VA has become a leader in advancing CIH through its Whole Health Initiative, there remain many barriers, especially for rural patients. Our team has co-developed, with multiple-levels of VA advisors (including rural patients), an innovative telehealth evidence-based intervention that builds upon our team's previous research. The Reaching Rural Veterans: Applying Mind-Body Skills for Pain Using a Whole Health Telehealth Intervention (**RAMP**) project strategically coalesces multiple evidence-based CIH self-management strategies to address Veterans' BPS needs and overcome existing barriers. Comprised of pain education, mindfulness, pain specific exercises, and cognitive behavioral strategies, the program is cohesive and scalable, and designed to meet the needs of VA interest holders. RAMP is a 9-week program comprised of group sessions including pre-recorded expert-led education videos, mind-body skill training and practice, and facilitated discussions. For the preparatory phase (UG3/Phase 1) we will conduct 1) **advisor engagement activities** including identifying and developing new community partnerships and using mixed methods data collection from multiple levels of advisors (n=35-50 patients, community partners, VA healthcare system leaders and staff), guided by the established RE-AIM/PRISM framework, to learn about key factors that can affect long-term adoption; and 2) conduct a **pilot study** of 40 rural VA patients with chronic pain to assess the feasibility of delivering RAMP (pilot) in terms of recruitment and engagement, intervention fidelity and adherence, data collection, and other key metrics. For the UH3/Phase 2, we will conduct a randomized hybrid type 2 effectiveness-implementation multi-site pragmatic clinical trial of RAMP compared to Usual Care, among rural patients (n=500) in the VA healthcare system. UH3/Phase 2 Aim 1 will assess the relative effectiveness of RAMP in terms of the **primary effectiveness outcome** of pain interference at 3 and 6 months and **secondary outcomes** including opioid use and other HEAL recommended outcomes. In UH3/Phase 2 Aim 2 we will work iteratively with multiple levels of advisors (from UG3/Phase 1) to evaluate intervention implementation strategies used in the trial and adapt these strategies to scale up RAMP within the national VA healthcare system. This will include: a) conducting mixed-methods assessments of advisor and randomized trial participant views of implementation-related barriers and facilitators, resource needs, and other RE-AIM/PRISM domains; b) working with advisors to co-create additional plausible strategies for overcoming barriers to implementation of RAMP; and c) conducting budget impact analyses using models informed by advisor views to inform future decision making.
